7.1 Study Design

This is a prospective observational study. We will prospectively enroll a cohort of 50 UC patients who have achieved an adequate response to tofacitinib at a dose of 10mg bd and whose dose is being reduced to 5mg bd following a routine flexible sigmoidoscopy. Colonic

tissue and blood samples will be collected at study entry, and patients' disease course will be followed-up through routine care.

Week 44 has been chosen for the primary endpoint, as 44 weeks post dose de-escalation was used as the endpoint in OCTAVE Sustain.

Primary endpoint:

• Biomarkers, clinical markers and histological markers associated with ongoing treatment with 5mg bd in the absence of steroids at week 44.

Secondary Endpoints

• Biomarkers, clinical markers and histological markers associated with steroid free endoscopic remission at routine endoscopy at week 44

Biomarkers / outcome measures will include:

- Clinical status (SCCAI)
- CRP and faecal calprotectin (as part of routine care)
- Histological markers of disease activity (Nancy histological index) (as part of routine care)
- STAT activation in peripheral blood mononuclear cells
- Cytokine expression in peripheral T cells
- Gene signatures in colonic biopsies

Guy's and St Thomas' MHS

NHS Foundation Trust

Flow Diagram

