We have the opportunity to systematically collect tissue from patients with UC treated with tofacitinib, as such we will undertake to track the mucosal immune response by multiparametric flow-cytometry study on endoscopic biopsies of the 50 patients within the BRITE study. These biopsies will be excess to these required to undertake the agreed experiments as part of the original study proposal – hence this proposal is of added benefit and will not detract from the funded study. This will facilitate flow cytometric immune monitoring of the architecture of the mucosal immune system (T cells, B cells and the myeloid compartment) at the point of de-escalation. Patients will subsequently be followed to relapse or the end of the study, whichever comes first, and tissue resampled to investigate the longitudinal changes in immunophenotype in the context of response to therapy. Similar immune monitoring has proved crucial at defining immune signatures in SARS-CoV-2 infection (15). This study is complementary to the work being performed in the original BRITE proposal and will provide more information on the effect of the drug on immunophenotypes and identify immunological signatures of response and or relapse – allowing a precision approach to drug selection.

6 Trial objectives and purpose

This is an investigator-initiated study with an overarching objective to identify biochemical and genetic markers of patients more likely to flare after tofacitinib dose reduction. It is hoped that this will eventually allow us to target continued higher dosing of 10mg bd at those patients who are most likely to benefit from it and avoid its use in patients in whom it is potentially unnecessary. Thereby, it would enable using the drug in a safer, more effective and more economical manner.

Primary objective:

• To identify biochemical, histologic and genetic markers predictive of ulcerative colitis flare in patients on tofacitinib commencing on maintenance 5mg BD dosing.

Secondary objectives:

- To identify clinical characteristics predictive of ulcerative colitis flare in patients on tofacitinib commencing on maintenance 5mg BD dosing.
- To identify predictors of endoscopic activity at week 44

7 Study design & Flowchart

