9.3 Schedule of Assessment for each visit

Patients in whom the treating team is planning to reduce their Tofacitinib from 10mg BD to 5mg will be referred for consideration of inclusion in the study.

- 1. Screening phone call
 - a. Information regarding the study provided
 - b. Inclusion/exclusion criteria reviewed
 - c. Patient information sheet, and consent form sent to patient in the mail or via e-mail.
- 2. Routine baseline endoscopy
 - a. Informed consent gained and form signed, prior to the endoscopy.
 - b. Baseline clinical data collected
 - c. Endoscopy performed and biopsies taken from rectum and sigmoid, to be sent for:

Guy's and St Thomas' Miss

NHS Foundation Trust

- i. Histological assessment of disease activity (Nancy Histological Index)
- ii. Genetic analysis
- iii. Future exploratory analysis
- d. Blood collection, to be sent for:
 - i. Routine clinical bloods (FBC, CRP, LFTs, U&E)
 - ii. STAT activation in peripheral blood mononuclear cells
 - iii. Cytokine expression in peripheral T cells
- e. Faecal calprotectin submitted
- 3. Flare (SCCAI \geq 5)
 - a. Should a clinical flare occur, patients will be encouraged to contact our IBD advice line as per current standard of care.
 - b. Routine and study blood tests, stool, and endoscopic tests will be initiated, as per standard of care, and the decision on how to manage the clinical flare will be taken by the treating team. Additional study biopsies will be taken at the time of the endoscopy.
- 4. Routine clinical visits
 - a. These will occur as per the treating team's discretion, with testing performed accordingly.
- 5. Week 44
 - a. In patients who remain on tofacitinib at week 44, routine clinical assessment will occur.
 - b. Tests performed will be
 - i. Routine endoscopy and biopsies, sent for:
 - 1. Histological assessment of disease activity (Nancy index) (part of routine care)
 - ii. Study biopsies, sent for:
 - 1. Genetic analysis
 - 2. Future exploratory analysis
 - iii. Routine blood collection, to be sent for:
 - 1. Routine clinical bloods (FBC, CRP, LFTs, U&E)
 - 2. Study blood tests will also be taken at this time point
 - iv. Routine faecal calprotectin

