9.6 End of Study Definition

The end of the trial will be deemed as date of final database lock and completion of analysis of laboratory samples collected from participants.

NHS Foundation Trust

10 Laboratories

Routine tests including blood tests (FBC, CRP, U&E, LFTs), and faecal calprotectin, will be performed as per standard of care at baseline, week 44, and at the treating team's discretion.

The Nancy Histological Index will be used to score histological disease activity, as per standard of care, at baseline and week 44.

Study specific tests of STAT activation, peripheral T cell cytokine expression, and genetic signature exploration will occur at baseline and flare or week 44.

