14.2 Statistical analysis

[name], clinical research fellow in gastroenterology, will perform the statistical analyses.

Baseline variables will be presented as either mean and standard deviation or medians and inter quartile range, depending on the normality of the data.

Receiver operator curves will be generated to determine optimal cut-offs for continues variables, predictive of disease flare.

Kaplan-Meier curves will be generated to allow comparisons of subdivisions of patients based on genetic and biochemical variables, using determined cut-offs.

Univariate and Multivariate analyses will be performed on clinical, biochemical and genetic variables to establish predictors of disease flare.

15 Ethical considerations

This is a non-interventional, observational study. Approvals will be sought from REC and HRA. Patients will need to provide informed consent to participate, and the only data collected from patients which occur in addition to standard of care are the additional tissue and blood samples collected at baseline and at week 44 for genetic, immune cell and cytokine analyses. Decisions regarding patient's care will have no relation to the study and will be directed by the patient's care team. Data collection and monitoring will occur in accordance with the rules and regulations set out above. The study design, management, undertaking, analysis and dissemination of results have had patient involvement, via a patient representative who sits on our project approvals board.

16 Financing and Insurance

Guy's and St Thomas' NHS Foundation Trust will take primary responsibility for ensuring that the design of the study meets appropriate standards and that arrangements are in place to ensure appropriate conduct and reporting are adhered to. King's College London as co-sponsor also provides cover under its No Fault Compensation Insurance, which provides for payment of damages or compensation in respect of any claim made by a research subject for bodily injury arising out of participation in a clinical trial or healthy volunteer study (with certain restrictions).

17 Reporting and dissemination

It is intended that the results of the study will be reported and disseminated at international conferences and in peer-reviewed scientific journals. A manuscript of the final study results will be submitted to an IBD specific journal (IBD or JCC) or to the IBD section of a general gastroenterology journal (Gut, Gastroenterology or CGH).

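### The primary endpoint is a treatment decision made by clinicians who are not masked to CRP, calprotectin and the Nancy index, and the reason for a treatment change is not recorded, so non-flare changes count as failures and can inflate these markers

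*Protocol*

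**What the plan says.** All references are to the protocol.

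- **Objective (section 6):** "To identify biochemical, histologic and genetic markers predictive of ulcerative colitis flare in patients on tofacitinib commencing on maintenance 5mg BD dosing".
- **Primary endpoint (section 7.1):** "Biomarkers, clinical markers and histological markers associated with ongoing treatment with 5mg bd in the absence of steroids at week 44". No SCCAI, endoscopic or biochemical criterion is attached.
- **Candidate markers (section 7.1):** the list includes "CRP and faecal calprotectin (as part of routine care") and "Histological markers of disease activity (Nancy histological index) (as part of routine care").
- **When the routine tests are done (section 10):** bloods and calprotectin "will be performed as per standard of care at baseline, week 44, and at the treating team's discretion".
- **Who decides treatment:** at a flare, "the decision on how to manage the clinical flare will be taken by the treating team" (section 9.3, item 3). In general, "Decisions regarding patient's care will have no relation to the study and will be directed by the patient's care team" (section 15).
- **Visits between baseline and week 44 (section 9.3, item 4):** "These will occur as per the treating team's discretion, with testing performed accordingly".
- **Data collected (section 13.1):** a change of treatment appears only in the flare list, beside the time point, SCCAI, CRP, calprotectin and, if done, the endoscopic Mayo score. No reason is listed. The week-44 list contains neither the current tofacitinib dose nor steroid use.
- **Analysis (section 14.2):** ROC cut-offs and univariate and multivariate models, all for disease flare.

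The contents list carries a heading on masking, but the body of the protocol has no such section.

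**The concern.** A prognostic study needs an outcome established independently of the predictors. Here the outcome is what clinicians did, and those clinicians have three of the predictors in front of them. If a symptom-free patient is taken off the 5mg bd dose or given steroids because a calprotectin or histology result came back high, that patient fails the endpoint and the marker is credited with predicting a relapse that was never observed. The proper name for this is outcome determination with knowledge of the predictor.

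Changes made for an adverse event have a related effect. Section 12.2 allows withdrawal from the drug for adverse events and intercurrent illness, and such a patient also fails the endpoint without a flare. If these changes are unrelated to the markers, they dilute true associations instead of inflating them.

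At stake is the interpretation of any positive finding for CRP, calprotectin or Nancy. It could reflect biology, clinical behaviour or both, and the listed data would not tell which.

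**Working it through.** The protocol gives no power, event rate or effect size, so there is no stated figure to reproduce. The check has three parts.

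**1. Does the structure allow the mechanism?**

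- Outcome: treatment status (section 7.1).
- Outcome decided by: the treating team (sections 9.3 and 15).
- Predictors known to that team: CRP, calprotectin and Nancy are routine-care results (sections 7.1 and 10), and no masking is described.
- Timing: biopsies are taken and calprotectin is submitted at the baseline endoscopy (section 9.3), and the dose is reduced after that procedure (section 7.1). Histology and stool results can therefore arrive once the reduction has been made, when acting on them counts as failure.

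**2. Can the recorded data separate the two kinds of failure?**

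| Situation | Where section 13.1 captures it |
|---|---|
| Change at a flare (SCCAI of 5 or more in section 9.3) | Flare list: time point, change, SCCAI; no reason |
| Change on a marker result, no symptoms | No listed field |
| Change for an adverse event, no flare | No listed field |
| Dose and steroid use at week 44 | No listed field, although they define the endpoint |

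A symptomatic change can be recognised from the SCCAI. A change without symptoms has no collection point.

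**3. How large could the effect be?** Every input here is an assumption; none is in the protocol. Take the 50 patients as 25 marker-high and 25 marker-low, with the same true failure risk f in both groups, so that the marker is worthless. Let clinicians change treatment on the marker alone in a fraction e of marker-high patients who would otherwise have succeeded.

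- Failure if marker-high: p1 = f + (1 − f)e. Failure if marker-low: p2 = f.
- Odds ratio = [p1/(1 − p1)] / [p2/(1 − p2)].
- Sensitivity = p1/(p1 + p2); specificity = (1 − p2)/[(1 − p1) + (1 − p2)]; AUC = their mean.
- Chance of p < 0.05: normal approximation for two proportions, 25 per group, two-sided.

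With f = 0.40:

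| e | p1 | Odds ratio | AUC | Chance of p < 0.05 |
|---|---|---|---|---|
| 0.10 | 0.40 + 0.60 × 0.10 = 0.46 | 0.852/0.667 = 1.28 | 0.53 | 6% |
| 0.20 | 0.40 + 0.60 × 0.20 = 0.52 | 1.083/0.667 = 1.62 | 0.56 | 13% |
| 0.40 | 0.40 + 0.60 × 0.40 = 0.64 | 1.778/0.667 = 2.67 | 0.62 | 39% |

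Over f from 0.3 to 0.5 and e from 0.1 to 0.5, the false odds ratio runs from 1.22 to 4.33, and the chance of a nominally significant result from about 5% to 71%. The bias is negligible if clinicians seldom act on the markers and serious if they often do.

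**The case against.** The other side has real force on several points.

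- **The behaviour is not documented.** The only route to a treatment change that the protocol sets out is symptomatic: SCCAI of 5 or more, a call to the advice line, tests, then a decision. A reader might infer that clinicians do change treatment on baseline results alone. No section says so; it is a possibility left open by routine reporting without masking. Entry also requires an adequate response in the treating team's opinion (section 8.1), so patients with evident activity at baseline may never enrol.
- **Other sections speak of flare.** The synopsis endpoint starts from a flare, the introduction contrasts symptomless patients with clinical relapse, and section 14.2 models flare. On those wordings a marker-only change is not an event. This stands, but it shows that the 7.1 endpoint does not match the rest. The secondary endpoint adds endoscopic remission, which is a disease measurement, but it does not repair the primary one.
- **Counting rules may belong in a SAP that is not shown.** True of censoring and event definitions. It does not cover a reason for change that the protocol's data list never collects.

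Three further inferences are tempting and unsupported. First, that the study's aim is to compare routine with novel markers and that this comparison is biased: sections 5 and 6 assess both sets as predictors and plan no head-to-head comparison. Second, that this is incorporation bias: no marker is part of the endpoint definition. Third, that STAT, cytokine and gene results will leak into care: section 15 separates care from the study, and the gene list in section 10.3 comes from comparing outcome groups, so it cannot exist before outcomes are known.

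**Conclusion.** The point holds in a limited form. The 7.1 endpoint records a treatment decision, the objective and analysis concern flare, the decision-makers are not masked to three candidate predictors, and section 13.1 cannot distinguish a change made without symptoms from a relapse. Marker-prompted changes could therefore inflate the apparent value of CRP, calprotectin and Nancy. The research assays would be affected only indirectly, through correlation with these.

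The direction for marker-prompted changes is clear; the size is unknown. The odds ratios of 1.22 to 4.33 show what the mechanism can do under assumed rates and do not estimate what will happen. The problem should be corrected because the reason for a change is most reliably captured when it is made, and no later analysis plan can count on recovering it.

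**What to change.** 1. In section 13.1, for every tofacitinib dose change or stop, steroid start or new UC therapy, at a flare visit or not, record the date, the SCCAI at that time and one coded reason: symptoms, new endoscopic activity, marker result without symptoms, adverse event, or other.
2. Add tofacitinib dose and steroid use to the week-44 data, since they define the endpoint.
3. Present the predictor analysis for flare-driven failure, using the protocol's own SCCAI threshold of 5 or more, beside the all-cause treatment-status endpoint. Treat non-flare changes as a separate category, or as a competing event in the time-to-event analysis. Do not rely on simple censoring alone: patients changed because of a high marker may be at higher risk of flare, so censoring them may be informative and bias the result the other way.

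The cost is one extra coded field (with date and SCCAI where not already collected), two week-44 items and one extra analysis. The flare analysis will have fewer events, which matters with 50 patients. Nobody's care changes.

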	dose commencing on maintenance tofacitinib therapy.
Primary objective	To identify biochemical and genetic markers predictive of
	ulcerative colitis flare
Secondary objective (s)	To identify clinical and disease characteristics predictive
	of ulcerative colitis flare
Number of Subjects/Patients	50 patients
Trial Design	Prospective observational study
Endpoints	1. Flare requiring drug discontinuation, surgery
	(colectomy) or addition of new therapy for ulcerative
	colitis.
	2. Endoscopic activity at week 44 endoscopy
Main Inclusion Criteria	Ulcerative colitis patients commencing tofacitinib
	maintenance dosing, undergoing endoscopy as part of
	their routine clinical care.
Statistical Methodology and Analysis	Receiver operator curves will be generated to determine
	optimal cut-offs for continues variables, predictive of
	disease flare.
	Kaplan-Meier curves will be generated to allow
	comparisons of subdivisions of patients based on genetic
	and biochemical variables, using determined cut-offs.
	Univariate and Multivariate analyses will be performed on
	clinical, biochemical and genetic variables to establish
	predictors of disease flare.

5 Introduction

Tofacitinib has been shown in large-scale randomised clinical trials to be an effective treatment for patients with moderate to severe UC that is resistant to both conventional treatment and to biologic therapy¹. In the few months it has been available in the UK, our unit has accrued some of the biggest experience in the country. Our initial experience and prospectively collected observational data suggest that the drug performs at least as well as clinical trial results would indicate.

Results from the OCTAVE clinical trial program led to the approval of an induction regimen of 10mg BD, with subsequent dose reduction in responders to 5mg BD after at least 8 weeks. This maintenance regimen was shown to maintain remission with greater efficacy than placebo¹. However, the clinical trial data further suggests that in patients who have previously failed anti-TNF therapy, the 10mg BD maintenance dose is superior to the 5mg BD dosing¹. Anecdotally, many clinicians are accordingly favouring continuing the 10mg bd dose in higher risk patients (biologic failures) for up to 52 weeks, rather than dropping to the maintenance dose at week 8.

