8.1 Subject inclusion criteria

- 1. Aged 18 years or over, either male or female
- 2. A history of ulcerative colitis, as defined by standard clinical criteria
- 3. Patients who are having their tofacitinib dose reduced from 10mg BD to 5mg BD in view of adequate response, as decided by their treating clinical team, and are undergoing routine endoscopy.

4. Sufficient English language skills to understand the patient information sheet and consent form.

8.2 Subject exclusion criteria (with justification if necessary – for example consider contra-indications to trial treatments, incompatible concurrent treatments, recent involvement in other research)

- 1. Patients undergoing dose reduction for reasons other than adequate response to 10mg bd (ie. active infection or VTE risk).
- 2. Patients being dose reduced without undergoing endoscopy

9 Study procedures

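### The synopsis and section 7.1 give non-equivalent primary outcomes, and section 14.2 analyses an undefined disease flare that is tied to neither

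*Protocol*

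**What the plan says.** Five places in the protocol bear on the outcome to be predicted.

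- **Synopsis (section 4), endpoints.** The first entry reads "Flare requiring drug discontinuation, surgery" and continues "colectomy) or addition of new therapy for ulcerative" colitis. This is an event defined by its treatment consequence. It is not labelled primary, but it heads a list of two, and the second entry (endoscopic activity at week 44) occupies the place of the section 7.1 secondary endpoint.
- **Section 6, primary objective.** "To identify biochemical, histologic and genetic markers predictive of ulcerative colitis flare in patients on tofacitinib commencing on maintenance 5mg BD dosing". Flare is not defined there.
- **Section 7.1, primary endpoint.** "Biomarkers, clinical markers and histological markers associated with ongoing treatment with 5mg bd in the absence of steroids at week 44". Flare is not mentioned.
- **Section 9.3, item 3.** The flare visit is headed "Flare (SCCAI \geq 5", a symptom threshold. The section adds that "the decision on how to manage the clinical flare will be taken by the treating team", so a patient can reach the threshold without any change of treatment.
- **Section 14.2.** "Univariate and Multivariate analyses will be performed on clinical, biochemical and genetic variables to establish predictors of disease flare". The ROC sentence also names disease flare. The Kaplan-Meier sentence names no outcome. The section 7.1 endpoint does not appear.

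No section links these wordings or ranks them.

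**The concern.** In a prediction study the outcome decides who is a case and who is a control. If section 14.2 is carried out as written, the endpoint that section 7.1 calls primary is never analysed, and the outcome that is analysed has no definition.

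The two stated outcomes also measure different things. The section 7.1 state counts any departure from 5 mg bd as failure, including stopping for intolerance, and it cannot see a flare that resolved before week 44. The synopsis event counts only flares with certain consequences. A marker of loss of disease control could look weaker or stronger depending on which is used, and two analysts following this protocol could report different case groups from the same 50 patients.

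**Working it through.** The protocol derives no sample size, power or event rate (section 14.1 says that a calculation is not possible), so there is no figure to reproduce. The check is to classify plausible patient courses under each wording.

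| Course after dose reduction | Section 9.3 heading (SCCAI 5 or more) | Synopsis endpoint 1 | Section 7.1 |
|---|---|---|---|
| 1. SCCAI reaches 5, settles with no treatment change; on 5 mg bd, no steroids at week 44 | flare | no event | success |
| 2. SCCAI reaches 5, steroid course finished before week 44; on 5 mg bd at week 44 | flare | depends on whether steroids count as new therapy | success |
| 3. SCCAI reaches 5, only response is dose re-escalation, still on the higher dose at week 44 | flare | not met on its wording | failure |
| 4. Tofacitinib stopped for an adverse event, colitis quiet | no flare | no event | failure |
| 5. SCCAI reaches 5, tofacitinib stopped because of it | flare | event | failure |
| 6. SCCAI stays below 5, on 5 mg bd, no steroids at week 44 | no flare | no event | success |

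Courses 5 and 6 agree throughout. Courses 1 to 4 do not, and the disagreement runs both ways. Courses 1 and 2 are section 9.3 flares that section 7.1 counts as successes. Course 4 is a section 7.1 failure with no flare at all. Course 1 alone gives one patient the labels flare, no event and success. Course 3 separates the two stated endpoints directly.

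**Fit with the planned methods.** Kaplan-Meier curves need a dated event. The section 7.1 endpoint is a status at one visit and supplies no event date. The synopsis event and the section 9.3 threshold can both be dated.

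**Fit with the data list.** Section 13.1 records time point, SCCAI and treatment alteration at flare. Its week-44 list contains neither the tofacitinib dose nor steroid use, which are the two components of the section 7.1 endpoint.

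**Illustration of size.** Apart from N = 50, every input here is an assumption. Suppose one biomarker with a true standardised difference of 0.9 between flare and non-flare, two-sided alpha 0.05, a true flare proportion p of 0.30 to 0.50, and a fraction m of true flares labelled non-flare by another definition (the pattern of course 1). Then:

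- labelled flares n1 = 50p(1 − m), and labelled non-flares n0 = 50 − n1;
- true flares among the labelled non-flares, c = 50pm / n0;
- observed difference d = 0.9(1 − c);
- power = Φ(d / √(1/n1 + 1/n0) − 1.96).

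For p = 0.40 and m = 0.20: n1 = 16, n0 = 34, c = 4/34 = 0.118, d = 0.794, √(1/16 + 1/34) = 0.303, and power = Φ(2.62 − 1.96) = 0.745.

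| p | m = 0 | m = 0.20 | m = 0.40 |
|---|---|---|---|
| 0.30 | 0.831 | 0.707 | 0.551 |
| 0.40 | 0.877 | 0.745 | 0.574 |
| 0.50 | 0.889 | 0.738 | 0.549 |

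The calculation ignores variance inflation within the mixed group and multiplicity. It assumes that relabelled flares carry the same marker levels as other flares; if mild flares that settle have intermediate levels, the loss is smaller.

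**The case against.** The strongest defence has four parts.

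- **The study is exploratory and observational, with no error rate to protect.** That lowers the stakes, but exploratory results still need a defined outcome to be interpreted or replicated.
- **A separate analysis plan may exist and may settle the definition before the data are seen.** It may. For that reason the documents do not support an inference that the definition will be chosen after looking at results. They do show a contradiction between protocol sections, which an analysis plan could resolve only by overriding one of them.
- **Section 14.2 agrees with the primary objective, since both speak of flare.** This is correct. The mismatch is with the section 7.1 primary endpoint, and the undefined term remains.
- **SCCAI of 5 or more is a visit heading, not an endpoint.** Also correct. A reader might infer three rival, incompatible endpoint definitions. The text supports two stated endpoints that are not equivalent, plus an analysis term whose only numeric anchor is that heading. Many patients will be classed alike under all of them.

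Three further readings go beyond the documents. A reader might infer that a patient entering with SCCAI of 5 or more has flared on day 0. However, section 9.3 describes a flare as something that occurs during follow-up, section 8.1 requires dose reduction "in view of adequate response, as decided by their treating clinical team", and nothing shows that such patients will enrol. A reader might expect course 3 to be common because the introduction discusses re-escalation after flare, but those figures describe recapture of response in an outside study, not how often re-escalation happens here. Finally, the gene-expression comparison is not wholly open: section 5, question 3, gives its own contrast, symptomless patients against those with clear clinical relapse. That contrast is a further symptom-based wording, which also needs aligning.

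**Conclusion.** The point stands as an internal contradiction in the protocol. The stated primary endpoint has no analysis in section 14.2, the synopsis gives a different outcome first, and the outcome that is analysed is undefined. This follows from the text alone and rests on no numerical assumption.

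Its reach is every ROC and regression analysis, and the Kaplan-Meier curves in so far as they share that outcome. Its numerical size cannot be derived, because the protocol gives no flare, re-escalation or discontinuation rates. Under the assumptions shown above, power for one biomarker falls from 83–89% to 71–75% if 20% of true flares are relabelled, and to 55–57% if 40% are. These ranges illustrate the mechanism and are not a forecast for this cohort. A single figure for lost discrimination would need error rates that the documents do not contain.

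**What to change.** Reconcile the passages before analysis.

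1. Name one primary outcome and use it in the same words in the synopsis, section 6, section 7.1, section 9.3 and section 14.2. The primary objective and section 14.2 both concern flare, and Kaplan-Meier needs a date, so a dated flare event is the natural choice. The exact clinical components are for the sponsor to decide.
2. Keep the week-44 state (on 5 mg bd, steroid-free) as a named secondary outcome with its own analysis in section 14.2.
3. For analysis only, state how four situations are classified: steroid courses, dose re-escalation, stopping tofacitinib without a flare, and withdrawal. This changes no patient's care.
4. Name the outcome in the Kaplan-Meier sentence, and align the gene-expression contrast in section 5 with the chosen definition.
5. Add to section 13.1 the date of dose reduction, the date and reason for stopping tofacitinib, and tofacitinib dose and steroid use at week 44.

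The cost is a protocol amendment and a small extension of the data form. No additional visit, sample or patient is needed.
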